#### 4.7 Replacement of Subjects

Patients who are randomized but do not receive study medication will be replaced. Patients who receive any study medication, even if they vomit immediately thereafter or cannot swallow the medication, will not be replaced.

## 5. Study Evaluations

### 5.1 Schedule of Evaluations

A flow chart of study evaluations is shown above, on page 10.

### 5.2 Description of Study Procedures

#### 5.2.1 Baseline procedures

- History and physical, including vital signs. History should include detailed history of present illness, including questioning about similarity of this episode with prior episodes, exposures to similar illnesses, and questioning about etiologies if not obvious.
- Physical examination should include all pertinent body symptoms.
- Vital signs should include height, weight, temperature, pulse, blood pressure, respiratory rate. All units should be metric.
- Baseline laboratory studies:
  - Required of all patients: CBC, biochemical profile, ECG
    - CBC to include: total RBC, total WBC count, absolute values for individual white blood cell types and platelet count.
    - Biochemical profile to include: albumin, alkaline phosphatase, ALT, AST, (total) bilirubin, BUN, calcium, chloride, CO2, creatinine, glucose, magnesium, potassium, sodium, total protein.
    - Standard 12-lead ECG
  - All patients ≥40 years of age and those with type 2 diabetes regardless of age: urinalysis, to include at a minimum: routine: dipstick tests for protein, glucose, ketones, blood, pH, specific gravity; microscopic: erythrocytes, leukocytes, bacteria, crystals, casts. Urinalysis is optional for patients <age 40.
  - For patients with diet-controlled type 2 diabetes mellitus: finger stick blood glucose
  - For women of childbearing potential, serum or urine pregnancy test (β-HCG)
- When drawing blood, a saline lock may be placed so that if the patient requires subsequent intravenous medications or hydration, he or she will not have to be stuck again.

Treatment can start once the urinary pregnancy test results are obtained and determined to be negative, and, for type 2 diabetics, finger stick results obtained and blood glucose is <200 mg/dL. Results of chemistries, CBC and urinalysis do not have to be available prior to start of study medication.

#### 5.2.2 Observation while in emergency department

To start immediately after administration of study medication:

- Intake and output hourly:
  - all oral and parenteral intake

- urination: number of voidings
  - vomiting: number of episodes
  - stool output: number, consistency (per scale in original protocol and per Bristol Stool Scale, Appendix I)
- Vital signs at least hourly and just prior to discharge: temperature, blood pressure, pulse, respiratory rate
- Questioning regarding adverse events: hourly and just prior to discharge
- Assessments of nausea: on signing informed consent, just prior to first dose of study medication, hourly, just prior to discharge from emergency department. A 5-point Likert scale will be used:
  - 0 No nausea
  - 1 Mild nausea
  - 2 Moderate nausea
  - 3 Severe nausea
  - 4 Nausea as bad as can be

- 12-lead ECG 4±0.25 hours after initial dose of study medication (regardless of whether dose was repeated in ED). If patient leaves ED <4 hours after dosing, an ECG should still be obtained just prior to discharge.
- Brief physical examination of pertinent systems prior to discharge

If a patient vomits ≥30 minutes after taking the first dose of study medication, requires rescue antiemetic or parenteral hydration, he or she will be considered a treatment failure. The patient will be followed according to the schedule above for a total of 4 hours from the time of first administration of study medication or until discharged home, whichever comes first. After that, for patients still in the emergency department or hospital, the patient will be followed per standard protocol, according to the patient's condition.

#### 5.2.3 Procedures after discharge from emergency department:

Any patient who has a post-dosing ECG showing QTc>500 msec must have a follow-up ECG within 72 hours of initial dosing showing resolution of the QTc prolongation. This may be performed on an inpatient or outpatient basis at the investigator's discretion. If the QTc does not decrease below 500 msec during initial follow-up, the medical monitor must be contacted to discuss further follow-up.

If a patient vomits from 30 minutes after taking the first dose of study medication until 24 hours after the first dose of study medication or requires rescue antiemetic or parenteral hydration during that period, even without vomiting, he or she will be considered a treatment failure. In that case, the only post-emergency department follow-up will be a call 72-96 hours after discharge from the emergency department to ascertain whether the patient's symptoms have

resolved, whether any adverse events occurred, and whether the patient required further medical follow-up, either in an emergency department or other medical facility.

Prior to discharge, patients who are treatment successes (i.e., no vomiting, no rescue medication and no parenteral hydration while in emergency department) will be given a diary card to record:

- all episodes of vomiting and bowel movements, with description of each bowel movement
- severity of nausea (on a 5-point Likert scale) three times a day: before breakfast or the time at which the patient usually eats breakfast, between 1:00-2:00 pm, and at bedtime
- any symptoms the patient may have related to gastroenteritis, such as chills, fever, abdominal pain
- adverse events
- medications taken, either for gastroenteritis (study medication and others) or other conditions

Patients will be contacted at least once daily for 4 days after discharge from the emergency department to question them about the presence of gastroenteritis symptoms and adverse events, to ask if and when they took study medication, and to ask whether they have returned to normal daily activities. The information recorded by the patient on his/her diary card will form the basis for data collected in the follow-up calls. If during the follow-up period, symptoms progress or worsen or new symptoms develop, the patient may be asked to return for further evaluation. If by day four after discharge (i.e., the day after the last dose of study medication), the patient still notes gastroenteritis symptoms, he or she will be instructed to return to see the investigator or his/her designate for further assessment. In addition, if the investigator is concerned that a patient may not be entering the data promptly and appropriately or as an added stimulus to data entry by the patient, the investigator may also contact the patient.

For patients returning due to persistent gastroenteritis 3 days after discharge from the ED, an interim history and physical examination will be performed. Laboratory studies may be performed if clinically indicated, and results of these studies will be entered into the CRF.

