cPrior to discharge, patients will be given diary pages to record their course after discharge. Patients will be contacted each day following treatment to a maximum of 4 days to determine whether they had further nausea and vomiting after leaving the emergency department, the occurrence and quality of bowel movements, including assessment using the Bristol stool scale (Appendix I), and the nature, occurrence and severity of other symptoms, whether they required further care for the acute gastroenteritis, and details regarding the continuation, if any, of the illness. If symptoms persist for 3 or more days after study entry, the patient is to be instructed to return for further evaluation.

dTo include all medications taken within 7 days prior to study entry, all treatments (including parenteral fluids) on the day of study entry, and all medication, including rescue medications, from the time of study entry through last follow-up.

ePatients are to receive the first dose of study medication within one hour of signing informed consent.

fPatients may take study medication daily for up to 3 days after study entry (maximum total of 4 doses, plus one additional if patient vomits within 15 minutes of first dose) if symptoms persist. Patients should stop taking study medication if symptoms have resolved, though they may resume study medication once daily if symptoms recur after discontinuation. Patients are not to take any remaining study medication after day 4. They will be given mailers to return any unused study medication.

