## 4. Study Design

### 4.1 Overview

Patients presenting to the emergency department who fulfill entry criteria will be asked to participate. A screening log will be kept listing all patients considered with reasons for patients not entering the study. Any patient whose information is reviewed in consideration for the study, even if not actually approached, is to be included in the screening log. The screening log will differentiate between those who are prescreened, i.e., who are reviewed but never progress to request for consent, from those who are screened, i.e., who are approached for consent, whether or not they actually sign consent or eventually participate in the study. Qualifying patients, once they have signed consent, will be stratified by age ( $\geq$  vs <age 18) and randomized 60:40 to RHB-102 or matching placebo. All patients will undergo laboratory testing and ECG, as specified below, once they have signed consent. However, only results of the pregnancy test (for women of childbearing potential) and a finger stick blood glucose (for patients with type 2 diabetes mellitus controlled by diet or oral medications) are required prior to treatment.

Patients will be started on oral fluids  $\geq$ 30 minutes after taking study medication (second dose for patients who receive 2 doses in ED) if they have not vomited during that period. Intravenous hydration should not be administered unless the patient has vomited or is clearly unable, after a reasonable period of time has elapsed since administration of study medication, to tolerate oral fluids.

At  $4\pm0.25$  hours after initial dosing, all patients are to have a repeat 12-lead ECG. Once stable, but not less than 4 hours after initial dosing, patients may be discharged from the emergency department. If a patient leaves the ED less than 4 hours after dosing, an ECG should be obtained if at all possible, even if the patient is leaving against protocol requirements.

On discharge, patients will be given an additional 3 doses of study medication to take at 24-hour intervals if nausea persists. Patients will be contacted daily for 4 days after discharge to determine their condition. Those patients who have persistent, worsening or recurrent nausea and/or vomiting during the follow-up period may be asked to come in for follow-up assessment by study personnel.

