### 4.2 Study Drug Administration

After results of the pregnancy test and/or blood glucose (when required) are obtained and determined to be negative/within acceptable limits and the patient is randomized, the investigator or a designate will administer the first dose of study medication under observation. If the patient vomits within 15 minutes, regardless of whether pill fragments are seen, a second dose of study medication will be administered by the investigator or a designate. If a patient retches but does not actually vomit any gastric contents, no second dose will be administered. If a patient vomits again, regardless of how long after the second dose of study medication, no further study medication will be administered.

Patients vomiting  $\geq$ 30 minutes after the first dose of study medication may receive rescue antiemetics, either parenterally or orally. In addition, patients with

severe nausea  $\geq$ 30 minutes after dosing with study medication and which in the investigator's opinion requires treatment may receive rescue medication. Metoclopramide 0.3 mg/kg, maximum dose 10 mg, administered intravenously will be the default rescue medication. Oral metoclopramide or other antiemetics administered either intravenously or orally may be used at the investigator's discretion. **However, patients are not to receive ondansetron or other 5-HT3 antagonists by any route for at least 24 hours after administration of study medication either in the ED or after discharge.** The following 5-HT3 antagonists are available in the US: alosetron (Lotronex), dolasetron (Anzemet), granisetron (Sancuso and others), ondansetron (Zofran, Zuplenz and others), palonsetron (Aloxi).

Oral fluids will be administered as tolerated once a patient has not vomited for 30 minutes after dosing with study medication (second dose for those patients receiving 2 doses in the ED). Only patients who do not tolerate oral fluids after an adequate attempt at oral hydration may receive parenteral hydration. Patients are not to receive intravenous hydration until it is clear to the treating physician that the patient is clearly in need of parenteral hydration.

Patients tolerating oral fluids will be discharged once deemed stable by the attending physician but not prior to 4 hours after dosing and repeat ECG.

Patients who do not tolerate oral fluids will receive parenteral hydration.

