#### 4.4.2 Serotonin syndrome

5-HT3 antagonists, including ondansetron, have been associated with serotonin syndrome. When given as a single agent, ondansetron overdose has been associated with serotonin syndrome. However, most reports of serotonin syndrome have been associated with concomitant use of serotonergic drugs (e.g., selective serotonin reuptake inhibitors (SSRIs), serotonin and norepinephrine reuptake inhibitors (SNRIs), monoamine oxidase inhibitors, mirtazapine, fentanyl, lithium, tramadol, and intravenous methylene blue). Some of the reported cases were fatal.

Symptoms associated with serotonin syndrome may include the following combination of signs and symptoms: mental status changes (e.g., agitation, hallucinations, delirium, and coma), autonomic instability (e.g., tachycardia, labile blood pressure, dizziness, diaphoresis, flushing, hyperthermia), neuromuscular symptoms (e.g., tremor, rigidity, myoclonus, hyperreflexia, incoordination), seizures, with or without gastrointestinal symptoms (e.g., nausea, vomiting, diarrhea). Patients should be warned about and monitored for the emergence of serotonin syndrome, especially with concomitant use of other serotonergic drugs. If symptoms of serotonin syndrome occur, discontinue RHB-102 and initiate supportive treatment.

All medications taken in the 7 days prior to study entry and from the time the patient arrives in the emergency room until he or she completes the study will be recorded in the case report form (CRF).

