#### 4.5 Duration of Treatment

On discharge, patients who have not had further vomiting and have not required rescue medication in the emergency department will be given 3 additional doses of study medication to take once daily if necessary. Patients will be instructed to take additional study medication if they are nauseated (whether persistent or recurrent) or have any vomiting. However, patients are not to take study medication more than 3 days after study entry. Thus, if a patient receives an initial dose of study medication in the emergency department, feels well the next day and does not take study medication, but subsequently has a recurrence of symptoms, that patient may not take the remaining dose of study medication on day 5. Rather, the patient should return for reassessment during the follow-up period.

Patients or their caregivers are to complete a diary each day for 4 days, recording episodes of vomiting, diarrhea, presence and severity of nausea, presence/development of other signs or symptoms related to the gastroenteritis, and occurrence of adverse events. This diary may be completed either on paper or through a web-based system. Alternatively, patients or their caregivers will be contacted daily for up to 4 days following study initiation (until symptoms have resolved) to ascertain whether the patient had further vomiting, other sequelae of the acute gastroenteritis or required further medical care for the gastroenteritis. If symptoms persist for 3 days after study entry, the patient will be instructed to return for further evaluation on the third or fourth day.

For patients discharged prior to 8:00 pm, the ED day diary page is to be completed. The ED day diary page is to include only information regarding events after discharge from the ED; information on events during the patient's ED stay is not to be repeated in the diary. For those discharged 8:00 pm to midnight, or later, diary information is to be recorded only on the follow-up diaries. But vomiting episodes and adverse events occurring between 8:00 pm and midnight the preceding day should be included in the information captured.

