#### 4.6 Discontinuation of Treatment

Patients may take study medication daily for up to 4 days (day 1 medication is the one or two tablets administered in the emergency department).

- If a patient vomits or otherwise receives rescue medication in the emergency department, he or she is not to receive additional study medication, even if nausea and/or vomiting is controlled with rescue medication.
- If the QTc interval at 4 hours after initial dose of study medication is >500 msec, study medication is to be discontinued.
- Patients experiencing recurrent nausea or vomiting after discharge from the emergency department and initial discontinuation of study medication due to resolution of symptoms may opt to resume study medication.

If a patient experiences an adverse event, regardless of relationship to study medication, which, in the investigator's opinion endangers or makes it difficult to evaluate the patient, the investigator may elect to have the patient stop study medication.

If once on study, a patient requires a medication which may prolong the QTc interval, he or she should not receive further study medication. However, evaluation of the patient should continue per protocol.

Patients may elect to discontinue treatment at any time.

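### Protocol 5.2.3 gives any 24-hour failure one late call, against the daily-contact text; read literally, home failures holding tablets have no scheduled contact until 76–100 hours after first dose

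*Protocol*

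**What the plan says.** Section 5.2.3 of the Protocol defines failure as vomiting, rescue antiemetic or parenteral hydration from 30 minutes to 24 hours after the first dose. It continues: "In that case, the only post-emergency department follow-up will be a call 72-96 hours after discharge from the emergency department". That call covers whether symptoms have resolved, adverse events and further medical care.

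Other text requires daily contact and does not exempt failures:

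- Study Assessments, note c: "Patients will be contacted each day following treatment to a maximum of 4 days to determine whether they had further nausea and vomiting".
- Section 4.1, repeated in SAP section 3.1: "Patients will be contacted daily for 4 days after discharge to determine their condition".
- A later paragraph of 5.2.3 has at least one contact a day for 4 days after discharge. It adds a question that the single call lacks: whether and when study medication was taken.

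On dosing after discharge, section 8 sends patients who have not failed in the ED home with three tablets. Section 4.5 tells them when to use these: "Patients will be instructed to take additional study medication if they are nauseated (whether persistent or recurrent) or have any vomiting". The failure stop in section 4.6 is confined to the ED: "If a patient vomits or otherwise receives rescue medication in the emergency department, he or she is not to receive additional study medication". Section 4.2 adds one further stop, for patients already redosed in the ED: "If a patient vomits again, regardless of how long after the second dose of study medication, no further study medication will be administered". Note f sets the end of dosing: "Patients are not to take any remaining study medication after day 4".

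**The concern.** The single-call rule fits a patient who fails in the ED and leaves without study drug. Its 24-hour window, however, runs well past the earliest discharge. A patient who goes home well and vomits at hour 10 was a success on leaving the ED and is a failure at 24 hours, so both follow-up rules apply. Unless already redosed in the ED, this patient still holds tablets and has been told to take them for nausea or vomiting. A site that follows the word *only* would reduce contact while the patient may be dosing.

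Two things are at stake. The first is safety follow-up of patients on drug. Section 4.4.2 says: "Patients should be warned about and monitored for the emergence of serotonin syndrome, especially with concomitant use of other serotonergic drugs". It names no means of doing so, and the late call does not ask about study-drug use. The second is comparability: if contact depends on the efficacy outcome, and the outcome is expected to differ by arm, adverse events may be collected with different intensity in the two arms. Sites may also resolve the conflict differently.

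The primary endpoint is not in question. These patients are already counted as failures.

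**Working it through.** The plan gives no figure of its own on this point, so the check is of timing and expected contacts.

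**Inputs.** Failure window 0.5 to 24 h after first dose, and call 72 to 96 h after discharge (5.2.3). Earliest per-protocol discharge 4 h after first dose (4.1, 4.2). Home doses once daily, nominally at 24, 48 and 72 h (4.1, 4.5). Expected failures 20% of 192 on RHB-102 and 40% of 128 on placebo (7.1).

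**Reach of the rule.** With discharge at 4 h, 24 − 4 = 20 of the 24 − 0.5 = 23.5 hours in the failure window fall after discharge. The rule is therefore not confined to ED failures.

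**Time of the call after first dose.** Discharge time + 72 h to discharge time + 96 h:

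- discharge at 4 h: 76 to 100 h
- discharge at 8 h: 80 to 104 h
- discharge at 12 h: 84 to 108 h
- departure at 2 h, against protocol: 74 to 98 h

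**Interval without a scheduled contact, discharge at 4 h.** Daily contact can still reveal the failure; the interval starts once it is known. The documents do not give that time, so 24, 28 and 34 h are assumed:

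| Failure known at | To earliest call | To latest call |
|---|---|---|
| 24 h | 76 − 24 = 52 h | 100 − 24 = 76 h |
| 28 h | 76 − 28 = 48 h | 100 − 28 = 72 h |
| 34 h | 76 − 34 = 42 h | 100 − 34 = 66 h |

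In each case the interval contains the nominal 48 h and 72 h doses, both optional. Dosing need not be over when the call comes. Note f allows doses through day 4, and the call window opens on day 4 whenever first-dose clock time + 76 h is below 96 h, that is, for first doses before 20:00.

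**Patients under the rule.** RHB-102: 192 × 0.20 = 38.4. Placebo: 128 × 0.40 = 51.2. Total 89.6. These include ED failures, who go home without tablets. The split between ED and home is not given, so the number holding tablets lies anywhere from 0 to these totals.

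**Planned contacts per patient.** Let *m* be the mean number of contacts for a non-failure and *f* the number for a failure, each the same in both arms. The difference between arms is (0.40 − 0.20) × (*m* − *f*) = 0.20 × (*m* − *f*). Take *f* = 1 for an ED failure and *f* = 2 for a home failure discovered at the day-2 contact.

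| *m* | Failures | RHB-102 | Placebo | Difference |
|---|---|---|---|---|
| 4 | all in ED | 0.8×4 + 0.2×1 = 3.4 | 0.6×4 + 0.4×1 = 2.8 | 0.6 |
| 4 | all at home | 0.8×4 + 0.2×2 = 3.6 | 0.6×4 + 0.4×2 = 3.2 | 0.4 |
| 2 | all in ED | 0.8×2 + 0.2×1 = 1.8 | 0.6×2 + 0.4×1 = 1.6 | 0.2 |
| 2 | all at home | 2.0 | 2.0 | 0 |

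The rows with *m* = 4 take the full four days in 5.2.3. The rows with *m* = 2 are an assumption, prompted by the synopsis and section 4.5, which run data collection only until symptoms have resolved, and by the synopsis statement that the illness usually lasts about a day.

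**The case against.** The strongest reply is that the gap exists on only one reading. Four places require daily contact, and under them nothing is missing. Section 5.2.3 can itself be read in sequence: a rule for failures, then diary cards for those who were successes while in the ED, then daily calls based on the diary. On that reading, anyone who leaves with tablets is called daily. This is workable and perhaps what was meant, but the failure sentence says 24 hours, not ED discharge, and no text subordinates it.

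The second reply is that other routes exist. Section 6 requires regular adverse-event assessment of all subjects until discharge after the last dose. Patients complete a diary, on paper or online, that covers adverse events and medication. The investigator may contact patients whose entries seem late, persistent symptoms prompt an instruction to return on day 3 or 4, and the late call asks about adverse events in retrospect. All of this stands as mitigation. However, section 6 sets no interval and refers back to the schedule in dispute, investigator contact is optional, and the return depends on symptoms. None fixes a contact for every home failure.

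The third reply concerns bias, and it largely stands. A reader might infer that the safety comparison is tilted in favour of RHB-102 by about half a contact per patient. The documents do not support that. The 0.4 to 0.6 is a ceiling, and the shortfall falls on placebo, the arm with more expected failures. That would tend to miss placebo events and make RHB-102 look worse. The effect on event counts cannot be derived.

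**Conclusion.** The conflict is real and should be resolved. Followed literally, 5.2.3 withdraws scheduled contact from patients who are still permitted to dose, until 76 to 100 hours after the first dose. That timing assumes discharge at 4 hours; later discharge moves it later, and departure before 4 hours, which the Protocol anticipates, moves it slightly earlier. If the failure becomes known at 24 to 34 hours, the interval to the earliest call is 42 to 52 hours. The number of patients affected is unknown.

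The difference in planned contacts between arms is a secondary matter: at most about 0.4 to 0.6 per patient, and close to zero if daily contact ends when symptoms resolve.

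Two stronger inferences should be resisted. One is that home failures are in fact left unmonitored: the daily-contact text, if followed, leaves no gap, and data may arrive by diary even if it is not. The other is that a serotonin-syndrome monitoring requirement is breached: section 4.4.2 says that patients should be monitored, gives no interval and is not tied to the calls in 5.2.3.

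**What to change.** In 5.2.3, limit the single call at 72 to 96 hours to patients who failed in the ED and hold no study tablets. State that every patient discharged with tablets keeps the daily contact, with both the adverse-event and the study-drug questions, even after failing at home. No new stopping rule is needed, since section 4.4.2 already calls for discontinuation if serotonin syndrome appears.

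The cost is one sentence, with no new visit or test. A home failure discovered at the day-2 contact gains 4 − 2 = 2 calls; the most any home failure gains is 4 − 1 = 3.

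Optionally, daily adverse-event contact could be kept for all dosed patients, which would also remove the difference between arms. On the 7.1 failure rates this adds at most 89.6 × 3 ≈ 269 calls over the trial, or 89.6 × 2 ≈ 179 if every failure were discovered at the day-2 contact.
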